#### 9.4.3 BASELINE DESCRIPTIVE STATISTICS

Descriptive statistics on patients' demographic characteristics and echocardiographic parameters will be reported as means and standard deviations for continuous variables and frequency counts for categorical variables. Rate to occurrence or prevalence data will be analyzed for this proposed study, and as such, repeated measures analysis from baseline are not applicable.

---

#### 9.4.4 PLANNED INTERIM ANALYSES

A 7 month planned interim analysis for the first 50 patients enrolled using the O'Brien-Fleming method will be conducted for cardiac death or myocardial infarction rate. Using an a priori alpha of .05, the adjusted alpha for the interim analysis will be 0.0054 and 0.0492 for the final analysis for consideration of frequency rates and obtained p-values at each analysis time point. Interim analysis outcomes will be used to assess trial efficacy, early evidence of harm, and safety to inform futility determinations and continuation considerations. Frequency rates on each outcome variable that exceed the non-inferiority margin of  $\pm 5\%$  for the interim analysis will result in temporary halting for further safety evaluations. The project statistician will conduct the planned interim analysis results will be reviewed by the study PI and research team.

---

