## 9.2 THE ALTERNATIVE HYPOTHESIS STATES THAT PATIENTS UNDERGOING SYNIVUS-DAPT TREATMENT WILL HAVE LOWER RATES OF MYOCARDIAL INFARCTION OR CARDIAC DEATH. SAMPLE SIZE DETERMINATION

An a priori power analysis was conducted for a one-sample binomial test with an alpha of .05 (one-tailed), beta of .05, constant proportion ( $p$ ) of .031, and assumed primary endpoint proportion of 0.0047 resulting in a needed sample size of 231.

The consideration of historical data on timing and incidence of myocardial infarction and stent thrombosis from published meta-analysis and related literature, the SCAAR registry and ACS subsets (De Luca, Dirksen, Spaulding, et al, 2012; Ellis, Colombo, Grube, et al, 2007; Palmerini, Biondi-Zocca, Riva, et al, 2012; Palmerini, Kirtane, Serruys, et al, 2012; SCAAR registry and ACS subset, 2016). Historic rates at 1-year follow up for ST showed variability ranging from 0.3 to 5.3%. Rates of MI range from 1.9 to 8.8%. A time-to-event bivariate exponential distribution function was used to determine criteria for sample sizes based on a 95% power determination resulting in a historic rate determination of 3.1%. Patients lost to follow-up will not be included in the final analysis, and additional patients will be recruited for study participation to reach the needed sample of 231.

The FDA has approved an initial phase of the investigation for 100 U.S patients. Accordingly, the sample size of N=100 for the initial phase is not statically based. Should approvals for study continuation be granted, the total sample size for subsequent phases will remain at 231, inclusive of subjects enrolled on this initial phase.

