#### 9.4.2 ANALYSIS OF THE PRIMARY ENDPOINT

*For primary endpoints:*

Prevalence rates of cardiac death and myocardial infarction will be determined for the sample. The binomial test will be conducted to test the significance of deviations from the expected distribution of observations dichotomized as “*did not occur*” or as “*occurrence*” for each outcome.

*For safety endpoints:*

Prevalence rates for safety outcomes including ischemia-driven (ID) target lesion revascularization, ID target vessel revascularization, target lesion failure, target vessel failure, all-cause death, and myocardial infarction will be evaluated with binomial tests.

The test formula to be used is as follows:

$$P(X) = C^n_k \ p^k (1-p)^{n-k}$$

All data will be screened for non-parametric statistical test assumptions. Accordingly, all dichotomous outcomes will be screened for exclusivity and appropriateness for inclusion in data analysis. Missing data, nonadherence and data lost to follow-up will be excluded from the final analysis.

The a priori alpha level for all statistical tests will be set at .05. To adjust for a potentially inflated family-wise error rate, the Bonferroni correction ( $\alpha/m$ ) will be applied for multiple tests with the same sample.

---

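### The O'Brien-Fleming pair 0.0054/0.0492 in section 9.4.4 does not fit a one-sided test with a look at 50 of 231 patients, though the practical effect is small

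*Combined protocol and SAP*

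**What the plan says.** Section 9.2 (Sample Size Determination) bases the trial on a "one-sample binomial test with an alpha of .05 (one-tailed), beta of .05", with a null proportion of .031 and an "assumed primary endpoint proportion of 0.0047 resulting in a needed sample size of 231". Section 9.1 gives the alternative as a rate below the null rate only.

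Section 9.2 also describes an FDA-approved initial phase of 100 patients, says that this number has no statistical basis, and adds that "the total sample size for subsequent phases will remain at 231, inclusive of subjects enrolled on this initial phase".

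Section 9.4.4 places a single interim analysis at 7 months on the first 50 patients enrolled, names the O'Brien-Fleming method, and sets the thresholds: "Using an a priori alpha of .05, the adjusted alpha for the interim analysis will be 0.0054 and 0.0492 for the final analysis". It assigns the look to efficacy, harm and futility, and adds a separate rule for a temporary halt. It does not state the sidedness of the two thresholds, the information fraction, the O'Brien-Fleming variant, or the sample size of the final analysis.

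Section 9.4.2 says: "The a priori alpha level for all statistical tests will be set at .05".

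**The concern.** O'Brien-Fleming thresholds depend on the sidedness of the test and on the fraction of the final information available at the look. Section 9.2 fixes both: one-sided, and 50 of 231. The stated pair matches neither. Its shape is that of a two-sided test with one look halfway, which would suit 50 of 100.

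Pre-specified thresholds are decision rules. If they do not follow from the design, nobody can tell which design they were meant for or which sample size carries the final alpha. An efficacy threshold that no interim result can cross also serves no purpose in the plan.

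**Working it through.** **Inputs.** One-sided alpha .05, p0 = .031, p1 = .0047, N = 231 (section 9.2); interim n = 50 and thresholds 0.0054/0.0492 (section 9.4.4).

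**1. The planned N confirms the one-sided design.** The arcsine formula gives
n = [(1.645 + 1.645) / (2(arcsin√.031 − arcsin√.0047))]² = 230.3, which rounds up to 231. The sample size therefore rests on one-sided .05 and 95% power.

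**2. Where the stated pair comes from.** Read as two-sided p-values, 0.0492 is z = 1.967 and 0.0054 is z = 2.782. The ratio is 2.782/1.967 = 1.4145, or √2. The classic O'Brien-Fleming shape is z₁ = c/√t at the look and z₂ = c at the end, so a ratio of √2 means t = 0.5. The shape is that of a two-sided look at half information. Exact integration for that design gives c = 1.977 and the pair 0.0052/0.0480, close to the stated pair but not equal to it.

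**3. Boundaries for the design in section 9.2.** t = 50/231 = 0.2165 and √t = 0.4652. For a one-sided test, the overall type I error is 1 − Φ₂(z₁, z₂; ρ = √t), where Φ₂ is the bivariate normal distribution function.
- Classic shape: setting this to .05 gives c = 1.6457 and z₁ = 1.6457/0.4652 = 3.537. The pair is 0.0002/0.0499.
- Lan-DeMets O'Brien-Fleming-type spending: 2[1 − Φ(1.960/0.4652)] = 2[1 − Φ(4.213)] = 0.000025 at the look, leaving 0.0500 at the end.

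Follow-up of 7 months, for an endpoint that runs to 13 months, would make the fraction smaller still.

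**4. What the stated pair spends (normal theory).** As one-sided values, 0.0054 and 0.0492 are z = 2.549 and 1.653.

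| Reading | Overall type I error |
|---|---|
| One-sided, 50/231 | 0.0527 |
| One-sided, 50/100 | 0.0509 |
| Two-sided, 50/100 | 0.0513 |

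**5. Whether the interim threshold can be met (exact binomial).** The best possible result is no events in 50: p = 0.969⁵⁰ = 0.207. To reach 0.0054 without an event requires n ≥ ln(.0054)/ln(.969) = 165.8, that is 166 event-free patients.

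**6. The final test at 231 (exact binomial, p0 = .031).**

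| Events | P(X ≤ k) |
|---|---|
| 2 | 0.0247 |
| 3 | 0.0707 |

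The rejection region is 2 or fewer events whether the final alpha is 0.0492, 0.0499 or 0.05.

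**The case against.** The strongest defence is that 50 is half of the 100-patient initial phase, so that half information was intended. One-sided Lan-DeMets spending at 50/100 gives 0.0056/0.0482, near the stated pair, and the stated pair overspends there by only about 0.001. This shows that the pair could be roughly usable one-sided at half information, and that no single pair is the right one until the variant is named. It does not rescue the text: section 9.4.4 does not tie the look to 100 patients, and section 9.2 gives that number no statistical basis and sizes the test at 231.

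A second defence is that nothing changes in practice. This largely stands. No efficacy threshold at 50 can be crossed, whether 0.0054 or 0.0002, and the region at 231 is the same under each candidate alpha.

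A third is that sections 9.4.2 and 9.4.4 do not conflict over alpha, since 9.4.4 starts from .05 and adjusts it. This is also fair: the specific clause modifies the general one, and only a cross-reference is missing.

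A reader might go further and infer that type I error is inflated because the trial tests at 100 and again at 231. The documents schedule no test at 100. As an illustration only, if one were added at 0.0492, no events in 100 would reject (0.969¹⁰⁰ = 0.0429). Rejecting on 0 of 100 or on 2 or fewer of 231 would then have exact type I error 0.0429 + 0.0247 − 0.0096 = 0.058, where 0.0096 is the chance of both. That is a reason to say plainly that 100 is descriptive. It does not describe the plan as written.

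**Conclusion.** The stated pair does not follow from the plan's own design, and the interim efficacy threshold cannot be met at 50 patients. As written, section 9.4.4 needs correcting.

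The point is minor. The nominal excess is 0.0527 against 0.05, a normal-theory figure that the exact binomial test does not realise. A reader might infer from the gap between 0.0054 and 0.0002 that a false early claim of efficacy is likely. It is not, because neither value is attainable at n = 50. If 231 is the only final test, the actual type I error is about 0.025.

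This rests on p0 = .031, on 231 evaluable patients, on one test of the composite endpoint before any Bonferroni division under section 9.4.2, and on information counted as patients.

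**What to change.** In section 9.4.4, do one of the following:
- Remove the efficacy boundary at 50 patients and use one-sided .05 for a single final test at N = 231. This is the simpler choice, since no efficacy boundary can operate at 50.
- Keep a boundary, but restate it with its sidedness, O'Brien-Fleming variant, information fraction and final N. For a one-sided test at 50/231 this is 0.0002/0.0499 (classic) or 0.000025/0.0500 (Lan-DeMets), with a note that it cannot be crossed at 50.

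In either case:
- Keep the look at 50 for harm and futility review, including the existing halting rule.
- State that any summary at N = 100 is descriptive, as a rate with an exact confidence interval, and is not a hypothesis test.
- Quote the same final alpha in sections 9.4.2 and 9.4.4.

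The cost is wording only. The cut-off at 231 stays at 2 events, so no power is lost.

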#### 9.4.5 SUB-GROUP ANALYSES

The *F* test of stability (or Chow test) for the coefficients of a panel model will be used to examine outcomes according to site and region and to test for the presence of individual effects.

$$F_{1\text{-way}} = \frac{(ESS_R - ESS_U) / (N - 1)}{ESS_U / ((T - 1)N - K)}$$

$ESS_R$  denotes the residual sum of squares under the null hypothesis and  $ESS_U$  the residual sum of squares under the alternative. Under  $H_0$ , the statistic  $F_{1\text{-way}}$  is distributed as  $F$  with  $(N - 1, (T - 1)N - K)$  degrees of freedom. Accordingly, the null hypothesis is as follows:

$$H_0 : \mu_i = 0, i = 1, \dots, N.$$

Additional subgroup analyses will be conducted to examine potential differences in women and ethnic/racial minorities.

---

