**Secondary Endpoints**

- Rate of cardiac death or myocardial infarction (SCAI definition) from 1 to 13 months post-index procedure in the overall enrolled “intent-to-treat” patient population
- Rate of Academic Research Consortium (ARC) definite/probable stent thrombosis (ST) involving SYNERGY™Stents from 1 to 13 months post-index procedure
- Rate of major bleeding (GUSTO severe/life threatening + moderate) from 1 to 13 months post-index procedure
- Ischemia-Driven (ID) Target Lesion Revascularization,
- ID Target Vessel Revascularization,
- Target Lesion Failure,
- Target Vessel Failure,
- All-Cause Death, and
- All-Cause Death or MI.

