**Angiographic Exclusion Criteria**

[figure not shown]
1. Target lesion(s) is located within a saphenous vein graft or an arterial graft
2. TIMI flow 0 (total occlusion)
3. Target lesion(s) is located in the left main

4. Potential Target lesion(s) that involve a complex bifurcation (i.e. bifurcation lesion requiring treatment with more than one stent)
5. Thrombus, or possible thrombus, present in the target vessel (by visual estimate)
6. Patients requiring a treatment of more than two native epicardial vessels
7. More than three lesions in two epicardial vessels unless they can be covered by one stent.
8. In-stent restenosis of target lesion
9. Treatment of non-target lesions or lesions not treated with a Synergy™ stent
10. Subject who did not receive Boston Scientific IVUS guided stent implantation and assessment
11. Any target lesion that has not been post dilated and has not had post dilatation IVUS
12. Patients who do not meet the following IVUS success criteria:
  - Target lesion(s) in which the stent cross sectional area is less than the distal reference cross sectional area and additional post-dilatation is not performed, followed by repeat IVUS.

\*\* Note: If the IVUS criteria is not met after the 2nd post dilatation the patient is excluded

Phase	Pilot
Description of Sites/Facilities Enrolling Participants:	The study will be conducted at HonorHealth System within the Phoenix, Arizona metropolitan area, and two institutions outside of the HonorHealth System. All Institutions within the HonorHealth system will collectively be considered a single “site”. All sites have recognized expertise with Boston Scientific IVUS guided stent implantation and will use IVUS to perform the procedures. The study will not be conducted outside the United States and its territories. Additional sites may be added pending enrollment rates.
Description of Study Intervention:	This is a study designed to follow patients whom have received IVUS-guided Implantation of the SYNERGY™ Stents and discontinued DAPT at 1 month.
Study Duration:	24 Months
Participant Duration:	13 Months
Total Number of Patients:	231

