**Post PCI Follow up Visits**

Follow up visits will occur at 30 and 60 days post PCI, and 7 and 13 months post PCI

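### The panel F test for site and region in section 9.4.5 is not fully specified and does not suit one rare yes/no outcome per patient

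*Combined protocol and SAP*

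**What the plan says.** Section 9.4.5 of the combined protocol and SAP names an F test of stability (Chow test) for a panel model, which "will be used to examine outcomes according to site and region and to test for the presence of individual effects". It prints the statistic, its degrees of freedom (N-1, (T-1)N-K) and a null hypothesis that every individual effect is zero. Only the two residual sums of squares, ESS_R and ESS_U, are explained. The index running to N shows that N counts units, but not whether these are patients, sites or regions.

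Other sections bear on the choice:

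- Section 9.4.2 tests "deviations from the expected distribution of observations dichotomized as" occurred or did not occur, for each outcome. Its Bonferroni correction "will be applied for multiple tests with the same sample".
- Section 9.4.3 says that rate or prevalence data will be analysed and that repeated measures analysis from baseline does not apply.
- The synopsis (description of sites) lists one hospital system and two outside institutions, all in the United States. "All Institutions within the HonorHealth system will collectively be considered a single" site, and "Additional sites may be added pending enrollment rates". It names no regions and gives no site sizes.
- Section 9.2 gives an "assumed primary endpoint proportion of 0.0047 resulting in a needed sample size of 231", tested against a rate of .031. It also describes an initial phase of 100 patients.

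**The concern.** A panel F test assumes several observations per unit and roughly normal residuals. Here each patient contributes one yes/no value, and the plan expects about one event in the whole trial. A statistician following section 9.4.5 must first decide what N, T, K and region mean. One reading gives no statistic at all. The workable reading gives a statistic whose F reference distribution can fail when almost all outcomes are zero.

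This is the only test the plan specifies for differences between sites. What is at stake is whether the site comparison in the report is valid and reproducible. In particular, a single event at a small site could be reported as a significant site difference.

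**Working it through.** **Inputs.** From section 9.2: 231 patients, or 100 in the initial phase; event rates .0047 (assumed) and .031 (comparison). From the synopsis: three sites. Assumptions: the site splits, since the documents give none, and K=0.

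**The plan's own figure.** Section 9.4.5 states no number. The 231 of section 9.2 reproduces with the arcsine formula at one-sided alpha .05 and power .95: [(1.645+1.645) / (2·asin√.031 − 2·asin√.0047)]² = 230.3, rounded up to 231. Expected events are 231 × .0047 = 1.09 and 231 × .031 = 7.16.

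**Degrees of freedom by reading.**

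- Patients as units, one outcome each: N=231, T=1. The denominator is (1−1)×231 − K = −K, which is 0 or negative, so no F exists.
- Sites as units with equal sizes: N=3, T=77. The degrees of freedom are 2 and (77−1)×3 = 228, which is 231 − 3.
- Sites as units with unequal sizes: no single T exists. The usual unbalanced one-way F, with total patients minus sites (again 228), is needed, but it is not what is printed.

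**One event, sites as units.** Let M be all patients and n the size of the site with the event. Then ESS_R = 1 − 1/M, ESS_U = 1 − 1/n, and F = [(ESS_R − ESS_U)/2] / [ESS_U/(M−3)]. With two equal small sites, the exact (Fisher-Freeman-Halton) p is the chance that the one event falls at either of them.

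| Split | ESS_R | ESS_U | F | F-test p | Exact p |
|---|---|---|---|---|---|
| 171/30/30 | .9957 | .9667 | 3.42 | .034 | 60/231 = .26 |
| 191/20/20 | .9957 | .9500 | 5.48 | .0047 | 40/231 = .17 |
| 80/10/10 | .9900 | .9000 | 4.85 | .0098 | 20/100 = .20 |

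**Type I error with no true site difference.** All outcomes were enumerated at nominal 5%. Trials without events, where F is 0/0, count as non-rejections.

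| Split of 231 | F test, rate .0047 | Exact test, rate .0047 | F test, rate .031 |
|---|---|---|---|
| 77/77/77 | .0085 | .0008 | .0403 |
| 91/70/70 | .0050 | .0010 | .0433 |
| 111/60/60 | .0028 | .0035 | .0359 |
| 131/50/50 | .0212 | .0022 | .0451 |
| 151/40/40 | .0157 | .0038 | .0457 |
| 171/30/30 | .1097 | .0083 | .0533 |
| 191/20/20 | .0744 | .0093 | .0590 |

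At rate .0047 the F test exceeds 5% only at the two most unequal splits. At .031 it is close to nominal throughout. With a Bonferroni threshold of .025 (m=2), 171/30/30 falls to 1.35% and only 191/20/20 stays above its threshold, at 7.4%.

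**Initial phase, 100 patients, rate .0047.** Expected events are 0.47. The chance of no event, leaving F undefined, is .9953^100 = .62 (for 231 patients it is .34). Type I error at 80/10/10 is 6.2%.

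**The case against.** The strongest reply is that sites are the obvious units. Any software fitting an unbalanced one-way model would use total patients minus sites, so the undefined symbols are mostly a matter of notation. On that reading the test does respond to site. With 77 patients per site, seven events all at one site give p=.0006, and a 3/2/2 spread gives p=.86. At five of the seven assumed splits the test is conservative at the expected event rate. Bonferroni would remove the excess at one of the other two.

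Most of this stands and limits the point. It does not rescue the method. The plan does not state the site-level reading, region has no definition at all, and the failure occurs in a realistic case: one dominant site and one event.

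Two stronger inferences are tempting and should be resisted.

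- Since "Follow up visits will occur at 30 and 60 days post PCI, and 7 and 13 months post PCI", a reader might take the four contacts as T and conclude that the statistic tracks event timing and ignores site. Section 9.4.3 rules out repeated measures from baseline, and nothing in the documents describes coding the outcome contact by contact.
- A reader might insert one site's size as T for every site and claim that the p-value can be moved at will. That is not how an unbalanced model is fitted.

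**Conclusion.** The point holds and its weight is low. Section 9.4.5 prescribes a method whose terms are undefined and whose panel structure the data do not have. On the natural reading it can turn one event at a small site into a nominally significant site difference (p=.034 or .0047, against exact p=.26 or .17).

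The size rests on assumed site splits. Error above 5% at the .0047 rate appears only at 171/30/30 and 191/20/20 among the seven splits of 231, and at 80/10/10 in the 100-patient phase. The figures therefore do not support a claim that the test is badly calibrated in general.

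Nor do the documents support an inference that the trial's conclusion is at risk. No decision is tied to this test, the primary binomial test does not use it, and section 10.3 keeps safety committee review of each site's serious adverse events.

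**What to change.** Delete the panel F test, its formula and its null hypothesis from section 9.4.5. Replace them with:

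> For each site (HonorHealth System counted as one site), the number of participants, the number with cardiac death or MI from 1 to 13 months, and the rate with exact (Clopper-Pearson) 95% CI will be reported. If sites are compared by a test, a Fisher-Freeman-Halton exact test will be used. A non-significant result will not be reported as evidence that sites are alike.

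Define region or delete it. The Bonferroni rule, the choice of analysis population and the sex and race/ethnicity subgroups should stay out of this edit, because the defect shown here does not concern them.

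The cost is SAP wording only. No new data are needed and the replacement is simpler to run. The gain is validity, not detection: with one event the exact test was not below .05 at any split examined. At 77/77/77 it takes four events all at one site (p=.035; three give p=.108).

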#### 9.4.6 TABULATION OF INDIVIDUAL PARTICIPANT DATA

Individual participant data will be listed by each study outcome following the procedure to study cessation at 13 months. Any occurrence of cardiac death, myocardial infarction, and stent thrombosis prior to this time will be documented accordingly.

---

#### 9.4.7 EXPLORATORY ANALYSES

No additional exploratory or auxiliary analyses are planned for the investigation.

---

